Objectives	
Primary Objective
 
To assess the feasibility of treating patients with sequential pembrolizumab and SBRT in patients with metastatic urothelial carcinoma who have progressed on platinum based chemotherapy
 
Secondary Objectives
 
 1) To determine the safety of the combination of SBRT and pembrolizumab in patients with platinum-refractory metastatic urothelial carcinoma 2) To determine the anti-tumor efficacy of the combination of SBRT and pembrolizumab in patients with platinum-refractory metastatic urothelial carcinoma 
Exploratory Correlative Objectives
 
 1. To determine PD-L1 expression on tumor cells and tumor immune infiltrating cells in archival tumor specimens and correlate these findings with clinical outcomes 2. To evaluate the tumor mutational profile and burden by tissue based next generation sequencing (MI-Oncoseq) of fresh and/or archival tissue and correlate with clinical outcomes 3. To evaluate the tumor immune infiltrate of tumor tissue by gene expression profiling using CIBERSORT/TIMER and correlate these findings with clinical outcome
Number of Subjects	20

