1.4 Correlative Studies

Correlative studies comprehensively evaluating the tumor immune profile and mutational profile will be performed as described below. We plan to evaluate the following:

1) Evaluation of PD-L1 expression on the tumor cells and tumor infiltrating lymphocytes and correlation of these levels with clinical response to treatment

In the IMvigor 210 trial, PD-L1 expression on immune cells infiltrating tumor tissue did correlate with response. Twenty-six percent of patients whose tumor immune cells were highly positive by IHC responded whereas only 8% of patients whose tumor immune cells were PDL1 negative had a response. While displaying an important trend, PD-L1 expression is not a perfect biomarker, as evidenced by the fact that 2% of patients in the PD-L1 negative group had a complete response to atezolizumab [15].

2) Evaluate tumor mutational profile and burden by tissue based next generation sequencing (MI-Oncoseq) and correlate with clinical outcomes

Recent studies have shown that tumor mutational burden may predict for response to checkpoint inhibitors with a higher mutational load corresponding to improved efficacy. [16], [17]. In addition, specific mutations may predict for improved responses to immunotherapy as evidenced by the improved survival seen in patients with mismatch repair deficient colon cancer treated with pembrolizumab [18]. We will co-consent subjects to the University of Michigan tumor sequencing protocol MI-Oncoseq. Fresh and/or archival tumor tissue and germline tissue will undergo genomic profiling. We will also offer patients an optional biopsy at progression to look for changes in the tumor genome.

3) Evaluation of the tumor immune infiltrate by gene expression profiling (CIBERSORT)/TIMER using RNASeq data

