2.3 Correlative Objectives

1. To determine PD-L1 expression on tumor cells and tumor immune infiltrating cells in archival tumor specimens and correlate these findings with clinical outcomes
2. To evaluate the tumor mutational profile and burden by tissue based next generation sequencing (MI-Oncoseq) of fresh and/or archival tissue and correlate with clinical outcomes.
3. To evaluate the tumor immune infiltrate of tumor tissue by gene expression profiling using CIBERSORT/TIMER and correlate these findings with clinical outcome.

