6.2 Time and Events Table

All assessments have a window of \pm 5 business days except for imaging/tumor measurements where a window of \pm 7 business days will apply.

Study Calendar

	Screening period (within 28 days)	C1 D1 ¹	SBRT (will commence no later than initiation of cycle 2) ³	C2 D1	C3 D1	C4 D1	Week 12	C5 D1	Cycles per std frequency for drug Every 12 weeks	End of Treatment	Follow-up (every 12 weeks for up to 24 months) ⁵
Informed Consent for FAST	X										
Informed Consent for MI-Oncoseq ⁴	X										
Archival Tissue identified	X										
Serum and Plasma banking	X ²										
Optional Biopsy at Progression										X	
History and Physical	X	X		X	X	X		X	X	X	
ECOG PS	X	X		X	X	X		X	X	X	
Tumor Measurements	X						X			X	X
Toxicity Evaluation	X	X		X	X	X		X	X	X	
CBC with diff and platelet count	X	X		X	X	X		X	X	X	
Comp metabolic panel	X	X		X	X	X		X	X	X	
Amylase/Lipase	X							X		X	
TSH, free T3, free T4 (IF clinically indicated: FSH, LH, ACTH)	X							X		X	
HIV, Hepatitis B Surface Antigen	X										
Pregnancy test for WOCBP	X										
CT Chest	X						X			X	X

CT or MRI Abdomen/Pelvis	X						X			X		X
Pembrolizumab		X		X	X	X		X	X			
SBRT			X									

¹Cycles are 21 days in duration.

² Serum and plasma banking will be collected C1D1 prior to first dose

³SBRT cannot overlap with C1D1

⁴Optional

⁵ Continue follow-up after end of treatment is for patients who discontinue study treatment for reasons other than progressive disease or death AND patients who continue on treatment past 17 cycles. These patients should continue to be followed by imaging every 12 weeks with standard of care CT chest, abdomen/pelvis until documentation of progressive disease, death, withdrawal of consent, or initiation of a new anti-cancer treatment for up to 2 years.

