11.0 STATISTICAL CONSIDERATIONS

11.1 Study Design/Study Endpoints, Sample Size and Accrual

The primary aim of this study is to determine the feasibility of treating patients with metastatic urothelial carcinoma who have progressed after platinum based chemotherapy with sequential pembrolizumab and SBRT. Treatment success will be defined as completion of 4 cycles of pembrolizumab and at least one course of treatment of SBRT within 15 weeks from first dose of pembrolizumab. The trial will define the combination treatment as feasible if 70% of the patients receive the treatment as defined. With 20 evaluable patients, if 14 out of 20 (70% [95% Confidence Interval: 50% - 90%]) achieve successful treatment then the trial will conclude that further evaluation of sequential pembrolizumab and SBRT should be explored. A patient is evaluable for feasibility and safety if they receive at least one dose of pembrolizumab. Patients who achieve a complete response prior to SBRT are not evaluable for feasibility. Non-evaluable patients will be replaced. With accrual of 1-2 patients per month the trial accrual is expected to take up to 24 months.

Secondary endpoints will include efficacy and safety. Efficacy will be measured using the following endpoints: best overall response by RECIST and Immune Related Response Criteria and progression-free survival by RECIST and Immune Related Response Criteria. Safety endpoints will measure the frequency and severity of grade 3-5 drug-related adverse events of the combination of SBRT and pembrolizumab.

Correlative plans are described separately below.

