11.2 Data Analyses Plans

The primary analysis will report the count, proportion and corresponding 95% binomial confidence interval of evaluable patients who completed 4 cycles of pembrolizumab and at least one course of treatment of SBRT within 15 weeks from first dose of pembrolizumab.

The best overall response (CR + PR) by RECIST and Immune Related Response Criteria will be reported separately with counts, proportions and corresponding 95% binomial confidence intervals. Progression-free survival endpoints will be described with medians and Kaplan-Meier plots using product-limit estimates and associated 95% confidence intervals using RECIST and Immune Related Response Criteria separately. Frequency and severity of drug-related adverse events will be described. Each of the secondary endpoints will be described in the evaluable population and in the population who achieve treatment success as defined in the primary endpoint.

Correlative Analyses

PD-L1 expression on tumor cells and immune cells infiltrating tumor, and CIBERSORT/TIMER gene expression profiling correlatives will be analyzed with association to clinical outcomes using exact chi-square tests, t-tests, or Kaplan-Meier methods as is appropriate for each independent covariate and clinical outcome. Tumor mutational status and burden by tissue based next generation sequencing (MI-ONCOSEQ) results will be descriptive.

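### The objective is to correlate mutational profile and burden with clinical outcomes, but section 11.2 makes these results descriptive and specifies no analysis linking them to outcome

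*Combined protocol and SAP*

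**What the plan says.** The aim appears three times. The synopsis lists it under "Exploratory Correlative Objectives". Section 2.3, objective 2, reads: "To evaluate the tumor mutational profile and burden by tissue based next generation sequencing (MI-Oncoseq) of fresh and/or archival tissue and correlate with clinical outcomes". Section 1.4, item 2, repeats it: "Evaluate tumor mutational profile and burden by tissue based next generation sequencing (MI-Oncoseq) and correlate with clinical outcomes". The rationale given there is that a higher mutational load may predict response to checkpoint inhibitors.

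Section 11.1 refers the reader onward for the correlative plans, which are in section 11.2 under Correlative Analyses. That paragraph has two sentences. The first covers PD-L1 expression and CIBERSORT/TIMER profiling, which "will be analyzed with association to clinical outcomes using exact chi-square tests, t-tests, or Kaplan-Meier methods as is appropriate" for each covariate and outcome. The second covers the sequencing results: "Tumor mutational status and burden by tissue based next generation sequencing (MI-ONCOSEQ) results will be descriptive".

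The study calendar in section 6.2 lists "Informed Consent for MI-Oncoseq" with a footnote marking it optional. The number of patients expected to be sequenced is not given.

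**The concern.** An objective that says *correlate with outcomes* needs an analysis that relates the marker to an outcome. Section 11.2 supplies one for two of the three correlative objectives and, in the next sentence, treats the third differently. An analyst could tabulate mutational burden on its own, comply fully with section 11.2, and never relate it to response or progression-free survival.

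What is at stake is modest but specific. With only a handful of responders, any apparent relation between burden and outcome will depend heavily on the scale, the cut-point and the endpoint. If none of these is fixed in advance, a later analysis would serve a stated aim but its method would be chosen after the data were seen.

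**Working it through.** **The plan's own figure.** No figure is stated for the mutational correlative. The only sample-size figure is in section 11.1: "With 20 evaluable patients, if 14 out of 20 (70% [95% Confidence Interval: 50% - 90%]) achieve successful treatment". A Wald interval reproduces it: 0.70 ± 1.960 × √(0.70 × 0.30 / 20) = 0.70 ± 0.201, or 49.9% to 90.1%. It has no bearing on this point.

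**The passages side by side.**

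| Correlative | Aim (synopsis, 1.4, 2.3) | Analysis in 11.2 |
|---|---|---|
| PD-L1 expression | Correlate with outcome | Association, methods named |
| CIBERSORT/TIMER immune infiltrate | Correlate with outcome | Association, methods named |
| Mutational profile and burden | Correlate with outcome | Descriptive; no outcome, grouping, scale, cut-point or statistic named |

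No other section supplies the missing link for the third row. Section 10.1 lists sequencing only as a possible use of the tissue.

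**Does sample size explain the difference?** Not by itself. Section 1.4 describes the CIBERSORT/TIMER work as a subproject of the OncoSeq analysis, so it draws on the same sequencing programme. If association methods are acceptable for that marker, small numbers alone do not justify withholding them from burden. The plan gives no other reason.

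**How much could an added analysis show?** These are illustrations, not figures from the plan. Assumptions: numbers sequenced of 20, 15 and 10; the 21% response rate that section 1.2 cites for pembrolizumab alone; two-sided 5% level; 80% power; normal approximation.

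- Expected responders: 0.21 × 20 = 4.2; 0.21 × 15 = 3.15; 0.21 × 10 = 2.1. Rounded: 4, 3 and 2.
- Half-width of the 95% interval for the responder versus non-responder difference, in SD units: 1.960 × √(1/r + 1/(n − r)), with r responders among n sequenced.
- Difference detectable with 80% power: (1.960 + 0.842) × √(1/r + 1/(n − r)). For n = 20: 2.802 × √(1/4 + 1/16) = 2.802 × 0.559 = 1.57 SD.
- Smallest detectable correlation (Fisher z): tanh(2.802 / √(n − 3)). For n = 20: tanh(2.802 / √17) = 0.59.

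| Sequenced | Responders vs others | 95% CI half-width | Detectable difference | Power for 0.8 SD | Detectable correlation |
|---|---|---|---|---|---|
| 20 | 4 vs 16 | 1.10 SD | 1.57 SD | 30% | 0.59 |
| 15 | 3 vs 12 | 1.27 SD | 1.81 SD | 24% | 0.67 |
| 10 | 2 vs 8 | 1.55 SD | 2.21 SD | 17% | 0.79 |

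Only very large effects would be detectable, so an added analysis would in practice be estimation with wide intervals.

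**The case against.** The strongest reply is that *descriptive* is not defined and need not exclude outcome. In the preceding paragraph, section 11.2 uses the same language for progression-free survival, which is to be described with medians, Kaplan-Meier plots and 95% confidence intervals. In that usage, burden summarised by response group, or Kaplan-Meier curves by burden group, would be descriptive. This stands. A reader might infer that the objective cannot be answered, or that the association will never be estimated; the documents do not support that. What they lack is any statement that burden or profile will be summarised against an outcome, and the contrast with the preceding sentence points the other way.

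A reader might also infer that any later association analysis would fall outside the plan. It would lack a pre-specified method, but correlating with outcome is a stated objective, so the inference goes too far.

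The reply continues that description is a defensible choice for an exploratory objective with about 20 patients and optional consent. That is fair, and the table above supports caution about testing. It is a reason to reword the objective if description is all that is meant, not a reason to leave the two statements in conflict.

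Finally, the optional consent does not cap the number sequenced at 20. Consent refusals lower it, but under section 5.10 patients not evaluable for feasibility are replaced, and nothing bars them from being sequenced. The 20 used above is the planned evaluable number, taken as an assumption.

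**Conclusion.** The mismatch is real. Three places promise correlation with outcome, and the analysis section, on its natural reading, provides none for mutational profile or burden. This is more than missing detail, because a stated analysis rule conflicts with a stated objective.

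Its weight is low. It concerns one exploratory objective of three. The feasibility rule and the secondary efficacy and safety analyses are untouched. The expectation of about 4 responders rests on two assumptions: that all 20 planned evaluable patients are sequenced, and that the response rate for pembrolizumab alone carries over to the combination.

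**What to change.** In section 11.2, under Correlative Analyses:

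- Add mutational burden, as a continuous marker, to the exploratory association analyses already planned for PD-L1 and CIBERSORT/TIMER. Report the difference between responders and non-responders with a 95% confidence interval, stating which of the two response criteria defines a responder.
- Show Kaplan-Meier progression-free survival by burden group, with the cut-point fixed in advance.
- Tabulate the mutational profile by best overall response, so that both halves of the objective are covered.
- Report the number of patients sequenced, and label all of this exploratory.

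The cost is a few lines of text and a small set of exploratory outputs, with no data beyond those already planned in consenting patients. The drawback is one more very imprecise comparison, which the intervals and the exploratory label should make plain.

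If the sponsor does intend description only, leave section 11.2 as it is and reword the objective in the synopsis, section 1.4 and section 2.3 to match. Either route removes the conflict; the first keeps the stated scientific aim.

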12.0 DATA AND SAFETY MONITORING

This trial will be monitored in accordance with the NCI approved University of Michigan Comprehensive Cancer Center Data and Safety Monitoring Plan.

The study team will meet quarterly or more frequently depending on the activity of the protocol. The discussion will include matters related to the safety of study participants (SAE/UaP reporting), validity and integrity of the data, enrollment rate relative to expectations, characteristics of participants, retention of participants, adherence to the protocol (potential or real protocol deviations) and data completeness. At these regular meetings, the protocol specific Data and Safety Monitoring Report form will be completed and signed by the Principal Investigator or by one of the co-investigators.

Data and Safety Monitoring Reports will be submitted to the University of Michigan Comprehensive Cancer Center Data and Safety Monitoring Committee on a quarterly basis for independent review.

